### 8.2.2 Safety Analysis

All treated subjects will be considered evaluable for safety. Skin irritation scores assessed in accordance with Appendix 14.11 will be reported for any subject who is scored with a 1 or more at any observation [baseline (screening day and treatment day), post-application/prior to 30 second, 10 minute, or 6 hour sampling procedures], in any category for any site.

Adverse events (including post treatment skin irritation scores of 3 in accordance with Appendix 14.11, will also be summarized. Summary tables will present incidence rates of adverse events by treatment group for all subjects who enter the treatment period. Listings of adverse events will be provided.

The statistical significance of differences in skin irritation between the three treatments will be evaluated using Fisher's exact test on skin irritation data summarized as follows: any reaction above zero (no reaction) on the skin irritation rating scale for any category (erythema, edema, rash, and dryness) will be considered a positive signal for that substance. If Fisher's exact test shows statistically significant skin irritation between the three treatments, a secondary analysis will be conducted to determine how the reactions differ.

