### 3. Study Design

#### 3.1 Study Type

This is a randomized, paired-comparisons design where each subject receives two of the planned treatments.

**Table 3.1:** Treatments, Anatomical Sites of Evaluation, Application and Dry Times and Coverage Areas (See Appendix 14.7 for detailed application instructions)

Treatment (Quantity/Volume)	Body Site	Application Time	Dry Time	Area of Coverage
ZuraPrep™ [REDACTED]	Abdomen (sebaceous poor)	30 seconds	3 minutes	5" x 5"
	Groin (sebaceous rich)	2 minutes	3 minutes	1.5" x 5"
ChloraPrep® [REDACTED] Scrub Teal® Tint, (positive control)	Abdomen (sebaceous poor)	30 seconds	3 minutes	5" x 5"
	Groin (sebaceous rich)	2 minutes	3 minutes	1.5" x 5"
ZuraPrep™ Vehicle, [REDACTED] (negative control)	Abdomen (sebaceous poor)	30seconds	3 minutes	5" x 5"
	Groin (sebaceous rich)	2 minutes	3 minutes	1.5" x 5"

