# 7. Assessment of Safety

## 7.1 Safety Parameters

The principal measures of safety will be the recording of skin irritation scores and the incidence of adverse events reported during the study.

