Comments: A minimum of 352 subjects will be treated bilaterally using the investigational study products, one positive control product and one negative control product to yield 320 readings each for the investigational study product and positive control product and 64 readings for negative control product for each of the two test sites (abdominal and inguinal regions).			

Date Issued: 07/13/16 [REDACTED]

Laboratory Project Identification No. 865-105  
Zurex Pharma, Inc. Project No.: ZX-ZP-0073

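### Skin irritation is compared by an unpaired three-group Fisher test although each subject receives two products, and no pairwise difference or interval is planned unless that test is significant.

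*Combined protocol and SAP*

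**What the plan says.** Section 7.1 gives irritation a leading role: "The principal measures of safety will be the recording of skin irritation scores", alongside adverse event incidence. Section 3.1 describes a paired design in which "each subject receives two of the planned treatments", and Section 3.3 puts one on each side of the body.

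Section 8.2.2 then sets the comparison: "The statistical significance of differences in skin irritation between the three treatments will be evaluated using Fisher's exact test". A product counts as positive for "any reaction above zero (no reaction) on the skin irritation rating scale for any category". The follow-up is conditional: it takes place if Fisher's test "shows statistically significant skin irritation between the three treatments, a secondary analysis will be conducted to determine how the reactions differ".

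Two outputs do not depend on the test. Irritation scores "will be reported for any subject who is scored with a 1 or more at any observation". For adverse events, which include irritation scores of 3, "Summary tables will present incidence rates of adverse events by treatment group for all subjects who enter the treatment period", with listings.

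The project sheet of 07/13/16, after Appendix 14.13, plans at least 352 subjects to give "320 readings each for the investigational study product and positive control product and 64 readings for negative control product" at each of the two anatomical regions. For irritation, the documents state no significance level, expected rate, power, unit of analysis or method for the follow-up. None of the eight protocol amendments changes this part of the plan.

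**The concern.** A non-significant test is weak evidence that two products irritate equally, and weaker still when the sample size was set for something else (Section 8.3 uses efficacy alone). Under Section 8.2.2 a non-significant result leaves a p-value and descriptive reporting. No planned output says how large an excess on ZuraPrep over ChloraPrep the data could still allow. Efficacy is treated differently: Section 8.2.1 plans intervals for rates and for differences between products without any gate.

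The choice of test adds to this. Most subjects carry ZuraPrep on one side and ChloraPrep on the other, so they are their own controls. Section 8.2.1 recognises this for log reductions by making subject a random effect, but Fisher's test on irritation treats the three groups as separate people. If skin reactivity is a trait of the person, that discards information and makes the test conservative.

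At stake is whether a principal safety measure ends in an estimate with limits or in a single p-value.

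**Working it through.** **The plan's own figure.** There is none for irritation. The only sample size calculation with stated inputs is for efficacy (Section 8.3): 77.8% against 70%, 80% power, 267 per active product. The two-sided 0.05 normal approximation gives n = (1.96·√(0.7·0.3) + 0.8416·√(0.778·0.222))² / 0.078² = 1.2479² / 0.006084 = 256, or 269 with continuity correction. Exact binomial power at n = 267 (success if at least 202 respond) is 82.1%. So 267 is reproduced, and it has no bearing on irritation.

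**Pair counts.** Let x, y and z be the numbers of ZuraPrep/ChloraPrep, ZuraPrep/vehicle and ChloraPrep/vehicle subjects. Then x + y = 320, x + z = 320 and y + z = 64. This gives x = 288, y = 32, z = 32, total 352, which matches the stated minimum.

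**Assumptions, none given in the documents.** Two-sided alpha 0.05; one yes/no result per subject and product; the minimum group sizes 320/320/64; ZuraPrep at twice a rate shared by ChloraPrep and vehicle.

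**The planned test.** With m positives in total, a table (a, b, c) has probability C(320,a)·C(320,b)·C(64,c)/C(704,m). The p-value sums all tables no more probable than the one observed. Power was obtained by full enumeration under independent binomials. The last column is a direct two-group Fisher test, 320 v 320, with no gate.

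| Other products v ZuraPrep | Three-group test misses | Direct unpaired test misses |
|---|---|---|
| 0.5% v 1% | 96.0% | 97.3% |
| 2% v 4% | 76.9% | 75.4% |
| 5% v 10% | 40.6% | 38.0% |
| 10% v 20% | 7.5% | 6.5% |
| 20% v 40% | 0.02% | 0.02% |

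In the three middle rows, dropping the gate but keeping an unpaired test gains 1.5, 2.6 and 1.0 points.

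**Sensitivity at 5% v 10%.** The three-group test misses 28.8% at alpha 0.10. It misses 37.3% if vehicle is doubled too, and 10.0% if abdomen and groin are counted separately (640/640/128) and treated as independent. Simulating the paired layout leaves its power at about 58–61%.

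**Within-subject comparison.** Take the 288 pairs, p₁ = 0.10, p₂ = 0.05 and binary correlation φ. The share positive on both sides is p₁₁ = p₁p₂ + φ·√(p₁(1−p₁)p₂(1−p₂)) = 0.005 + 0.0654φ. The discordant shares are 0.10 − p₁₁ and 0.05 − p₁₁. Exact McNemar power, two-sided 0.05:

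| φ | ZuraPrep only | ChloraPrep only | Power |
|---|---|---|---|
| 0 | 9.5% | 4.5% | 57% |
| 0.3 | 7.5% | 2.5% | 72% |
| 0.5 | 6.2% | 1.2% | 87% |

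Since p₁₁ cannot exceed 0.05, φ cannot exceed 0.045/0.0654 = 0.688.

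**Calibration.** With all three products truly at 5%, the three-group test rejects in only about 1–3% of trials once the pairs are correlated, against a nominal 5%.

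**What an interval would show.** With both active products at 5% and φ = 0.3, the paired 95% half-width is 1.96·√(2·0.05·0.95·0.7/288) = 0.030, or about ±3 percentage points.

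**The case against.** A reader might infer that a doubling of irritation on ZuraPrep would go unexamined in about 4 of 10 trials because of the gate. The documents do not support that, for four reasons.

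- **Not unexamined.** The Fisher test is itself a comparison of products. Scores of 1 or more are reported, and adverse events are tabulated by treatment, whatever its result. This stands. However, the score reporting is by subject and promises no rate by product, and irritation is stated to enter the adverse event tables only at score 3. Neither supplies the missing contrast.
- **No single miss rate.** The documents give neither irritation rate nor alpha. Four in ten belongs to 5% v 10% alone, and a doubling is missed anywhere from 96% of the time to almost never. Section 7.2 has scores recorded for each site, so the unit is open too. This stands, and only a range can be given.
- **The gate is not the main cause.** Removing it without pairing changes detection by 1 to 3 points; sample size is the main limit. This stands. The gain in power comes from pairing, and only if reactions on the two sides are correlated. At zero correlation the paired test (57%) is no better than the planned one (59%).
- **No declared misreading.** Section 8.2.2 nowhere says that a non-significant result means equal irritation, no success criterion rests on this test, and nothing forbids extra intervals. This stands as a limit on severity. A principal safety measure should still not depend on an analyst volunteering the estimate.

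**Conclusion.** The point holds as a fault in the choice and reporting of the irritation analysis. If the three-group test is not significant, the plan yields no ZuraPrep-ChloraPrep difference and no interval, and the test ignores the pairing that the design was built on.

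At 5% v 10%, the within-subject comparison gains about 11 points at binary correlation 0.3 (72% against 61%) and 26 at 0.5 (87% against 61%), and nothing at zero. These figures rest on assumed rates, alpha 0.05, one result per subject and product, and the minimum counts. The safety set may be larger, since recruitment continues until the efficacy counts are met (Section 4).

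The case for an interval does not depend on those assumptions: at any rate, a limit on the excess tells the reader more than a non-significant p-value. This should be changed, but it does not threaten the efficacy conclusions, and it does not show that irritation data would be withheld.

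**What to change.** In Section 8.2.2, remove the condition on the follow-up. Whatever the Fisher result:

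- Report, by product, the number and percentage with any post-treatment score above 0 in any category, and state the unit (one result per subject and product, with abdomen and groin also shown separately).
- Report ZuraPrep-ChloraPrep, ZuraPrep-vehicle and ChloraPrep-vehicle differences with 95% intervals. Take ZuraPrep-ChloraPrep within subject, from subjects who received both, with a paired interval and exact McNemar test. For the vehicle contrasts, use a method that allows for subjects contributing to both products.
- Keep the three-group Fisher p-value as descriptive, and state the significance level.

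If the analysis has already been run, add these as a supplementary table and record the change under Section 8.6.

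The cost is a few sentences and one table from data already collected. The intervals may look less reassuring than a p-value. Those against vehicle will be wide: with 64 vehicle subjects, even an unpaired test of 5% v 10% misses about 82% of the time.

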### 8.3 Sample Size Justification

The number of subjects for the active treatments (ZuraPrep™ and the active comparator) is based off of the following assumptions: the primary efficacy parameters are as defined above; the power is 80%; and the minimum responder rate for active substances is 77.8%. Using [REDACTED] for a single

proportion method, this requires 267 subjects per active treatment. The number 320 was used to make randomization blocking easier and to be conservative.

The numbers required for the inactive/negative control group were based on results from [REDACTED]. The sample size is designed to be sufficient to show there is a significant difference in responder rates between the active substances and inactive control at 30 seconds and 10 minutes and a significant difference in  $\log_{10}$  CFU/cm^2 reductions from baseline at 6 hours. Based on these assumptions, the sample size should be at least 40. A sample size of 64 was chosen for easier balance of factors during randomization. [REDACTED]  
[REDACTED]

#### **8.4 Subject Discontinuation Criteria**

The Investigator may discontinue individual subjects from the study at any time. Subjects may voluntarily withdraw from the study at any time. The Investigator will provide a written report on the appropriate CRF including the date and reason for discontinuation.

#### **8.5 Procedures for Accounting for Missing Data and Protocol Deviations**

Missing microbiological data at 30 seconds, 10 minutes, or 6 hours will be reported as missing; if the entire sample is missing the site will be treated as a nonresponder for that sample time. These subjects will be included in the mITT data set based on the criteria defined above. Details of any other missing data handling will be specified in the statistical analysis.

#### **8.6 Deviations to Statistical Plan**

Any deviation(s) from the original statistical plan will be described and justified in the final report.

### **9. Monitoring**

Zurex Pharma, Inc., as sponsor of this study along with the Investigator, is responsible for ensuring the proper conduct of the study with regard to protocol adherence and validity of the data recorded on the CRFs. Zurex Pharma, Inc. has, therefore, assigned a study monitor to this study. The progress of the study will be monitored by:

- Periodic on-site review
- Telephone communications and e-mail
- Review of CRFs and source documents (CRF serves as source document)

The Investigator will give the Zurex Pharma, Inc. study monitor direct access to source documents that support data on the CRFs and make available such records to authorized Zurex Pharma, Inc., quality assurance, IRB, and regulatory personnel for inspection and/or copying.

*Note: The Federal Privacy rule (HIPAA) specifically permits the use and disclosure of protected health information "to a person subject to the jurisdiction of the Food and Drug Administration (FDA) [e.g., study sponsor] with respect to an FDA-related product or activity for which that person has responsibility, for the purpose of activities related to the quality, safety, or effectiveness of such FDA-regulated product or activity" [45 CFR 164.512(b)(1)(iii)].*

## **10. Quality Control and Quality Assurance**

Zurex Pharma, Inc. and the Investigator are responsible for implementing and maintaining quality assurance and quality control systems through written standard operating procedures (SOPs) to ensure that this study is conducted and data are generated, documented and reported in compliance with the protocol, GCP and regulations cited in Section 1.4 of this protocol. Study monitoring may be carried out to accomplish this.

## **11. Ethics**

This study will be conducted in accordance with the principles that have their origin in the Declaration of Helsinki, 21 CFR 50 (Informed Consent) and 56 (IRBs). Laboratory operations will be conducted in accordance with 21 CFR 58 (Good Laboratory Practice for Nonclinical Laboratory Studies).

The study will start only after approval of the protocol and consent form by the IRB. The approval letter or notice must contain the IRB name and identification number, meeting date, and sufficient information to identify the protocol and informed consent by name and number that were reviewed. Zurex Pharma, Inc., prior to study initiation, must receive a copy of the IRB approval letter.

## **12. Data Handling and Record Keeping**

### **12.1 Study Personnel**

Prior to study initiation, the Investigator must provide Zurex Pharma, Inc. with a signed Investigator agreement as documentation of the Investigator's commitment to conduct the study according to the protocol and all applicable state and federal regulations.

## 12.2 Pre-Study Documentation Requirements

Prior to study initiation, the Investigator must provide Zurex Pharma, Inc. with the following documents:

- 12.2.1** Signed protocol including any amendments in place prior to study initiation
- 12.2.2** Curriculum vitae for the Investigator and any co-Investigators
- 12.2.3** IRB-approved informed consent form containing subject authorization for use and disclosure of Protected Health Information statement.
- 12.2.4** IRB study approval letter (including approval of the protocol, consent form, Investigator and study facility)
- 12.2.5** IRB name, location and board membership listing
- 12.2.6** Signed Investigator agreement
- 12.2.7** Signed Study Agreement and Confidentiality agreement

## 12.3 Completion of Case Report Forms

The Investigator will review all CRF entries for completeness and accuracy. If a correction is required, a single line must be drawn through the error. The person making the correction will initial, date, and provide a reason for the error (if not self-evident).

The Investigator must review and sign each CRF in a timely fashion following completion and make them available to the Zurex Pharma, Inc. study monitor for inspection. Before acceptance, the monitor will review the CRFs to ensure accuracy and completeness. The copies of CRFs will be submitted to Zurex Pharma, Inc. and the original will be maintained at the study site. In addition, any data queries prepared after the original CRFs have been completed must be answered promptly.

## 12.4 Final Report

The Investigator will prepare a final study report. The final report will be a record of the total study conduct and will be subject to review by Zurex Pharma, Inc. The final report will assess and summarize all data collected and include: test material identification, type of assay, randomization schedule, dates of study initiation and completion, CRFs, and data demonstrating neutralization effectiveness. A review of the final report by Quality Assurance, including compliance statements will also be included with the final report. A copy of the final report will be sent to the study sponsor.

## 12.5 Records, Reports and Retention Requirements

The Investigator will maintain study records for a minimum of 2 years following the date a marketing application is approved for the indication for which is being investigated, or, if no application is to be filed or if the application is not approved for such indication, until 2 years after the investigation is discontinued and FDA is notified. Records that must be maintained by the Investigator include, but are not restricted to:

- Signed study protocol, amendments, deviations
- IRB approval of protocol, consent form, authorization form, waiver of consent and/or authorization and amendments to any of these documents
- Applications to the IRB
- Signed consent and authorization forms
- Case report forms
- Adverse event reports
- Records of receipt, use or disposition of the study material
- Correspondence relating to the study
- Investigator Final Report
- Sponsor Final Report (if provided)

## 14.2 Study Summary

Pre-Study Preparation	Screening Phase		Treatment Phase	
	14 Day Washout Period	Screening Day	Abdominal Region	Groin Region
Staff reviews study protocol	Initiation of consenting process	Complete Screening Inclusion/ Exclusion Criteria form	Complete Treatment Inclusion/ Exclusion Criteria form	
Prepare consent form	Review study Consent Form and Inclusion/ Exclusion Criteria	Visual skin assessment	Visual skin assessment	
Obtain IRB approval	Review subject instructions	Collect screening baseline samples from abdominal and groin regions	Mark test areas, Collect baseline samples	
Recruit volunteers for screening phase (14 day washout / screening day)	Subject signs consent form	Count screening plates, determine which volunteers qualify for study	Apply test articles	
Prepare subject kits	Visual skin assessment (abdominal and groin regions)	Contact and enroll eligible subjects, schedule Treatment Day	Visual skin assessment, 30 seconds ( $\pm$ 5 sec.), 10 minute ( $\pm$ 30 sec.), 6 hours ( $\pm$ 30 min.) post-prep sample	Visual skin assessment, 30 seconds ( $\pm$ 5 sec.), 10 minute ( $\pm$ 30 sec.), 6 hours ( $\pm$ 30 min.) post-prep sample
	Dispense subject kits	Schedule for clipping, if needed, 48 hrs. prior to Treatment Day visit	Count Treatment Day Baseline plates, determine qualification and enroll additional subjects as required	Count Treatment Day Baseline plates, determine qualification and enroll additional subjects as required
	Schedule for clipping, if needed, 48 hrs. prior to screening visit	No bathing / showering 72 hrs. prior to Treatment Day visit		
	No bathing / showering 72 hrs. prior to screening visit			

### 14.3 Abdomen and Groin Diagram

Follow the randomization scheme for each subject for the exact placement of study materials.

Groin (anterior) – 1.5" x 5" area

Abdomen (anterior) – 5" x 5" area

#### 14.4 Randomization Scheme

##### Abdominal and Groin Sites Bilateral Sampling Procedure Configurations

###### GROUP 1

Key: A = ZuraPrep™ [REDACTED]  
B = ChloraPrep® [REDACTED]ator (Scrub Teal® Tint)  
C = ZuraPrep Vehicle (negative control)

Subject	Treatment	Site 1	Site 2	Site 3	Site 4
0001					
0002					
0003					
0004					
0005					
0006					
0007					
0008					
0009					
0010					
0011					
0012					
0013					
0014					
0015					
0016					
0017					
0018					
0019					
0020					
0021					
0022					
0023					
0024					
...					

Subjects will be numbered sequentially from 0001 to the number of subjects treated during the study.

Randomization will be performed by group issued prior to study initiation.

## 14.7 Treatment Application Instructions

## ZuraPrep™

1. **What is the primary purpose of the study?**

For more information, contact the Office of the Vice President for Research and the Office of the Vice President for Student Affairs.

10.1007/s00332-010-9000-0

10 of 10 pages

10.1002/anie.201907002

## Treatment Site Application Instructions

## Abdominal Test Site

1. Using repeated back-and-forth strokes of the sponge for thirty (30 ) seconds, completely wet the treatment area with test material.
2. Allow the area to air-dry for three (3) minutes. Do not blot or wipe away.

## Inguinal Test Site

1. Using repeated back-and-forth strokes of the sponge for two (2) minutes, completely wet the treatment area with test material.
2. Allow the area to air-dry for three (3) minutes. Do not blot or wipe away.

**ChloraPrep®** (Scrub Teal® Tint) (positive control)

1. *What is the primary purpose of the study?*

Digitized by [contact]

For more information, contact the Office of the Vice President for Research and the Office of the Vice President for Student Affairs.

11. **What is the primary purpose of the *Journal of Clinical Endocrinology and Metabolism*?**

Digitized by [contact]

© 2013 Pearson Education, Inc.

